## 11.1.2 Serious Adverse Events

An AE is considered serious if it results in any of the following outcomes:

- Death
- A life-threatening AE
- An AE that results in hospital admission or prolongation of existing hospitalization

- A persistent or significant incapacity or substantial disruption of the ability to conduct normal life functions
- A congenital anomaly/birth defect
- Important Medical Events that may not result in death, be life threatening, or require hospitalization may be considered serious when, based upon medical judgment, they may jeopardize the participant or subject and may require medical or surgical intervention to prevent one of the outcomes listed in this definition
- Potential drug induced liver injury (DILI) is also considered an important medical event. DILI is defined as the following:
  - o ALT or AST elevation >3x ULN AND
  - Total bilirubin >2x ULN, without elevated serum alkaline phosphatase AND
  - No other immediately apparent possible causes of AST/ALT elevation and hyperbilirubinemia, including, but not limited to, viral hepatitis, pre-existing chronic or acute liver disease, or the administration of other drug(s) known to be hepatotoxic.

Suspected transmission of an infectious agent (e.g., pathogenic or nonpathogenic) via study drug is an SAE.

Although pregnancy, overdose, and cancer are not always serious by regulatory definition, these events must be handled as SAEs.

Note: Hospital admission for elective pre-planned surgeries is not considered an SAE.

Disease Progression is considered a non-reportable event.

SAE reporting is required as soon as the participant signs consent and is registered. SAE reporting is required for 100-days after the participant's last investigational treatment or intervention. Any events that occur after the 100-day period and that are at least possibly related to protocol treatment must be reported.

inVentiv Health Clinical will manage SAEs using ARGUS, and all sites will send reports to inVentiv's safety team via email. Sites will not upload any reports directly into ARGUS.

#### SAE Reporting to BMS and inVentiv

Following the participant's written consent to participate in the study, all SAEs, whether related or not related to study drug, must be collected, including those thought to be associated with protocol-specified procedures. All AEs are to be followed until resolution, until a stable clinical endpoint is reached, or for 100 days after the last dose of study treatment, unless other anticancer therapy is initiated.

All SAEs must be collected that occur during the screening period. If applicable, SAEs must be collected that relate to any protocol-specified procedure (e.g., a follow-up skin biopsy). The Investigator should report any SAE that occurs after these time periods that is believed to be related to study drug or protocol-specified procedure.

If only limited information is initially available, follow-up reports are required. (Note: Follow-up SAE reports should include the same Investigator term(s) initially reported.)

Sites should complete SAE reports and then submit the reports per their local IRB requirements.

All SAEs should be followed to resolution or stabilization.

The Sponsor will ensure that all SAEs in the clinical database are reported to BMS and any applicable health authority during the conduct of the study.

# 11.1.3 Pregnancy

Female participants of childbearing potential must have a negative pregnancy test at Screening. An acceptable form of contraception must be used for up to 5 months post last dose by all female participants and for 7 months post last dose by all male participants (as detailed in Appendix 4). Following administration of study drug, any known cases of pregnancy in female participants will be reported until the participant completes or withdraws from the study. The pregnancy will be reported immediately by phone and by faxing/emailing a completed Pregnancy Report to the Sponsor (or designee) within 24 hours of knowledge of the event. The Investigator will follow the participant until completion of the pregnancy and must assess the outcome in the shortest possible time but not more than 30 days after completion of the pregnancy. The Investigator should notify the Sponsor (or designee) of the pregnancy outcome by submitting a follow-up Pregnancy Report on a Pregnancy Surveillance Form. If the outcome of the pregnancy meets the criteria for immediate classification of an SAE (e.g., spontaneous or therapeutic abortion [any congenital anomaly detected in an aborted fetus is to be documented], stillbirth, neonatal death, or congenital anomaly), the Investigator will report the event by phone and by faxing a completed SAE form to the Sponsor (or designee) within 24 hours of knowledge of the event.

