  - f. Aspartate aminotransferase (serum glutamic oxaloacetic transaminase)/alanine aminotransferase (serum glutamic pyruvic transaminase)  $\leq 2.5~X$  institution's upper limit of normal for participants with no concurrent liver metastases, OR  $\leq 5~X$  institution's upper limit of normal for participants with concurrent liver metastases
  - g. Serum creatinine < 1.5x OR creatinine clearance of at least 40
- 10. Women of childbearing potential must have a negative serum pregnancy test within 24 hours prior to the start of study drug. A woman of childbearing potential is defined as any female who has experienced menarche and who has not undergone surgical sterilization (hysterectomy or bilateral oophorectomy) or is not postmenopausal. Menopause is defined clinically as 12 months of amenorrhea in a woman over age 50 in the absence of other biologic or physiologic causes.

- 11. Women with child bearing potential and men with reproductive potential must be willing to practice acceptable methods of contraception.
- 12. Ability to understand and the willingness to sign a written informed consent document.
- 13. Willingness to undergo biopsy of metastatic site or site of unresectable disease prior to randomization.

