- f. Aspartate aminotransferase (AST) (serum glutamic oxaloacetic transaminase)/alanine aminotransferase (ALT) (serum glutamic pyruvic transaminase)  $\leq 2.5$  X institution's upper limit of normal for participants with no concurrent liver metastases,  $OR \leq 5$  X institution's upper limit of normal for participants with concurrent liver metastases
- g. Serum creatinine < 1.5x OR creatinine clearance of at least 40
- 10. Women of childbearing potential must have a negative serum pregnancy test within 24 hours prior to the start of study drug. A woman of childbearing potential is defined as any female who has experienced menarche and who has not undergone surgical sterilization (hysterectomy or bilateral oophorectomy) or is not postmenopausal. Menopause is defined clinically as 12 months of amenorrhea in a woman over age 50 in the absence of other biologic or physiologic causes.
- 11. Women with child bearing potential and men with reproductive potential must be willing to practice acceptable methods of contraception.
- 12. Ability to understand and the willingness to sign a written informed consent document.
- 13. Willingness to undergo biopsy of metastatic site or site of unresectable disease prior to randomization.

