#### **Contraception Guidance:**

#### Male Participants

• Are abstinent from penile-vaginal intercourse as their usual and preferred lifestyle (abstinent on a long term and persistent basis) and agree to remain abstinent

In addition, male participants must refrain from donating sperm for the duration of the study and for 7 months after the last dose of study intervention.

Male participants with a pregnant or breastfeeding partner must agree to remain abstinent from penile vaginal intercourse or use a male condom during each episode of penile penetration during the protocol-defined time frame and for 7 months after the last dose of study intervention.

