#### Female Participants

Female participants of childbearing potential are eligible to participate if they agree to use a highly effective method of contraception consistently and correctly as described in the table below.

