#### Sexual abstinence

Sexual abstinence is considered a highly effective method only if defined as refraining from heterosexual intercourse during the entire period of risk associated with the study intervention. The reliability of sexual abstinence needs to be evaluated in relation to the duration of the study and the preferred and usual lifestyle of the participant.

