#### NOTES:

- a) Typical use failure rates may differ from those when used consistently and correctly. Use should be consistent with local regulations regarding the use of contraceptive methods for participants participating in clinical studies.
- b) Hormonal contraception may be susceptible to interaction with the study intervention, which may reduce the efficacy of the contraceptive method. In this case, 2 highly effective methods of contraception should be utilized during the treatment period and for at least 5 months after the last dose of study intervention.

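### Section 11.1.3 words women's contraception after the last dose as up to 5 months, literally a ceiling, and no general minimum for women is stated elsewhere

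*Protocol*

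**What the plan says.** The general rule is in Protocol Section 11.1.3 (Pregnancy). For women: "An acceptable form of contraception must be used for up to 5 months post last dose by all female participants". The same sentence then gives the period for men and points to the appendix: "for 7 months post last dose by all male participants (as detailed in Appendix 4".

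Section 15.4 (Appendix 4) has three statements that bear on women:

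- **Female Participants.** Women of childbearing potential are "eligible to participate if they agree to use a highly effective method of contraception consistently and correctly". No period after the last dose is given.
- **Note b to the list of methods.** Where hormonal contraception may interact with study drug, "2 highly effective methods of contraception should be utilized during the treatment period and for at least 5 months after the last dose".
- **Sexual abstinence.** Abstinence counts as highly effective only if it means "refraining from heterosexual intercourse during the entire period of risk associated with the study intervention". No number of months is attached.

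Inclusion criterion 11, in Section 7.1 and in the synopsis, gives no duration. The SAP reproduces the synopsis and adds nothing on this point.

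**The concern.** The sentence in Section 11.1.3 is the instruction that sites work from, and it is the only general statement of how long women must continue contraception. Taken at its words, it bounds the period from above only. A woman who stopped a few weeks after her last infusion would not have broken it, although antibody would still be in her circulation: ipilimumab in either arm, and nivolumab as well in Arm A. A rule meant to prevent fetal exposure should state the shortest permissible period, because that is the part that protects. The same figure of 5 months is also worded in opposite directions in two places, as an upper limit in the general rule and as a lower limit in a special case. A site that consults the appendix for clarification may therefore come away less sure.

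**Working it through.** **Step 1: compare the texts.** No figure in the plan needs reproducing, since the point is one of wording.

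| Place | Whom it covers | Period after last dose | General minimum for women? |
|---|---|---|---|
| 11.1.3 | all female participants | 5 months, as an upper bound | no |
| Appendix 4, Female Participants | women of childbearing potential | none stated | no |
| Appendix 4, note b | possible hormonal interaction, two methods | 5 months, as a lower bound | no, special case |
| Appendix 4, abstinence | women relying on abstinence | period of risk, no number | no, one method only |
| Inclusion criterion 11 | women of childbearing potential and men with reproductive potential | none stated | no |

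None of the five rows gives a general minimum for women.

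**Step 2: show what lies between no minimum and 5 months.** The documents link no drug level to fetal risk, so only the presence of drug can be illustrated.

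Inputs:
- Mean half-life h = 15.4 days for ipilimumab (Section 8.1.1) and 25.7 days for nivolumab (Section 8.1.2).
- One month is taken as 30.4 days, so 3 months = 91.2 days and 5 months = 152 days.
- Assumption: single-exponential decline, so the fraction remaining relative to the end of dosing is 2^(−t/h).

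| t | Ipilimumab | Nivolumab (Arm A) |
|---|---|---|
| 30.4 days | 2^(−30.4/15.4) = 25.5% | 2^(−30.4/25.7) = 44.0% |
| 91.2 days | 2^(−91.2/15.4) = 1.6% | 2^(−91.2/25.7) = 8.5% |
| 152 days | 2^(−152/15.4) = 0.11% | 2^(−152/25.7) = 1.7% |

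Five months is 152/15.4 = 9.9 half-lives of ipilimumab and 152/25.7 = 5.9 of nivolumab. A full 5 months covers nearly all of the decline; 1 month does not.

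**The case against.** The strongest reply is that the intent is plain. The sentence makes contraception mandatory, and a ceiling with no floor would leave that obligation empty after the last dose. The natural reading is that use continues to the 5-month mark. Note b supports this, because a 5-month two-method rule makes little sense if the ordinary period could be shorter. The abstinence entry points the same way. A woman who uses contraception through month 5 satisfies all of these statements, so they can be reconciled. This stands, and it settles the intent. It does not supply the missing minimum, and a safety instruction should not depend on the reader to infer one.

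It is also true that the half-life figures do not measure the effect of the wording. They show why contraception is needed after dosing, and nothing in the documents suggests that any woman would stop early because of this phrase. The consent form and the Eligibility Checklist named in Section 13.2 are not among the documents and may state the period correctly.

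A smaller caution concerns Appendix 4. Its male section opens with a bullet that has no lead-in, and its list of methods is broken up, so some text may have been lost in conversion. The silence of the female paragraph is therefore somewhat weaker evidence than the wording of Section 11.1.3, which is complete.

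A reader might infer three stronger points. The documents do not support them:

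- **That a shorter period for women was planned.** The reasons above point to five full months.
- **That Appendix 4 gives men a general duration and leaves women out.** Its 7 months applies to sperm donation ("male participants must refrain from donating sperm for the duration of the study and for 7 months after the last dose") and to men with a pregnant or breastfeeding partner. The general period for men, like that for women, is in Section 11.1.3.
- **That inclusion criterion 11 conflicts with Appendix 4.** The criterion says that participants "must be willing to practice acceptable methods of contraception", while the appendix asks women for a highly effective method. Section 11.1.3 already ties the acceptable form to Appendix 4, so at most a cross-reference is missing.

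**Conclusion.** The point holds as a wording error in a safety rule. Section 11.1.3 literally sets a maximum where a minimum is needed, and no other text in the protocol or SAP gives women a general minimum. Severity is minor: the intended period can be recovered from context, the practical effect is unknown, and sample size, error rates and analyses are unaffected. The rule is written for all female participants, but its consequence falls on those of childbearing potential among the 24 planned, a number that the documents do not give. The drug-remaining figures rest on mean half-lives and single-exponential decline. Individual values will vary, the documents give no spread, and the figures indicate presence of drug, not risk.

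**What to change.** In Section 11.1.3, replace the upper-bound phrase for women so that contraception is required *during treatment and for at least 5 months after the final dose*. Repeat that duration in the Female Participants paragraph of Appendix 4, so that the section and the appendix agree.

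Section 11.1.3 now addresses all female participants, whereas Appendix 4 addresses women of childbearing potential. Limiting the rule to the latter would be sensible, but it changes who is covered and should be listed as a separate change.

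The cost is a wording amendment. Section 13.8.1 requires a formal amendment for any change, submitted to the IRB/IEC. Data collection and analysis are unaffected. Whether the consent form needs the same correction cannot be judged from these documents, so the sponsor should check it at the same time.

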## 11.1.4 Overdose

The Investigator must immediately notify the Sponsor of any occurrence of overdose with study drug. Overdose is defined as any dose higher than the dose specified to be administered in accordance with the protocol.

All overdoses should be reported to inVentiv as SAEs (see Section Error! Reference source not found.). Details of signs and symptoms, clinical management, and outcome should be reported, if available. Overdoses should also be captured as protocol deviations.

# 11.1.5 Disease-Related Events and/or Disease-Related Outcomes Not Qualifying as Adverse Events or Serious Adverse Events

Progression of the cancer under study, including deaths, as judged by the Investigator, is not considered a reportable event. Any suspected endpoint, which upon review from the Investigator, is not considered progression of the cancer under study must be reported as an SAE. Within 24 hours of determination that the event is not progression of the cancer under study, an SAE form should be forwarded to InVentiv Pharmacovigilance Group as described (see Section Error! Reference source not found.).

All deaths will be recorded on the Death eCRF page.

# 11.2 Unanticipated Problems/Non-Compliance

# **Unanticipated Problems**

An unexpected problem is any incident, experience, or outcome that meets all of the following criteria:

- unexpected (in terms of nature, severity, or frequency) given (a) the research procedures that are described in the protocol-related documents, such as the IRB-approved research protocol and informed consent document; and (b) the characteristics of the subject population being studied;
- related or possibly related to participation in the research (possibly related means there is a reasonable possibility that the incident, experience, or outcome may have been caused by the procedures involved in the research); and
- suggests that the research places subjects or others at a greater risk of harm (including physical, psychological, economic, or social harm) than was previously known or recognized.

An incident, experience, or outcome that meets the three criteria above generally will warrant consideration of substantive changes in the research protocol or informed consent process/document or other corrective actions in order to protect the safety, welfare, or rights of subjects or others. Examples of corrective actions or substantive changes that might need to be considered in response to an unanticipated problem include:

- changes to the research protocol initiated by the investigator prior to obtaining IRB approval to eliminate apparent immediate hazards to subjects;
- modification of inclusion or exclusion criteria to mitigate the newly identified risks;
- implementation of additional procedures for monitoring subjects:
- suspension of enrollment of new subjects;
- suspension of research procedures in currently enrolled subjects;
- modification of informed consent documents to include a description of newly recognized risks; and
- provision of additional information about newly recognized risks to previously enrolled subjects.

Only a small subset of AEs occurring in human subjects participating in research will meet these three criteria for an unanticipated problem. Furthermore, there are other types of incidents, experiences, and outcomes that occur during the conduct of human subjects research that represent unanticipated problems but are not considered AEs. For example, some unanticipated problems involve social or economic harm instead of the physical or psychological harm associated with AEs. In other cases, unanticipated problems place subjects or others at increased risk of harm, but no harm occurs.

It may be difficult to determine whether a particular AE is unexpected. This determination may require analysis of appropriate data on all subjects enrolled in the research. In addition, unanticipated problems may become apparent during continuing renewals, protocol violations,

deviations, complaints, injuries, or deaths. Investigators are required to promptly report to the IRB unanticipated problems involving risks to subjects or others. A report for an unexpected event should contain a clear explanation of why the event(s) was determined to be an unanticipated problem and a description of any proposed protocol changes or other corrective actions to be taken by the investigators in response to the unanticipated problem.

#### **Non-Compliance**

All investigators should comply with all applicable local, state, and federal regulations in the conduct of research involving human subjects. Non-compliance is defined as any violation of any regulation that governs human subject research, any deviation from the study protocol approved by the IRB, or any violation of any conditions imposed by the IRB on the approval of the study or conduct of the research. Investigators will also be informed when allegations of non-compliance are made during the study. Investigators are responsible for reporting in writing, all suspected incidents of non-compliance within 2 business days of discovery. Reports should be sent to inVentiv Health and the MSKCC research team for submission to the IRB and should include the incident, date of the incident, individuals involved, whether the incident requires further action, and corrective actions and procedures.

#### 12 STATISTICAL ANALYSIS

A Statistical Analysis Plan (SAP) will be prepared after the protocol is approved. This document will provide further details regarding the definition of analysis variables and analysis methodology to address all study objectives. The SAP will serve as a compliment to the protocol and supersedes it in case of differences.

The statistical evaluation will be performed using the Statistical Analysis Software (SAS®) Version 8.1 or higher (SAS Institute, Cary, NC). All data will be listed, and summary tables will be provided. Summary statistics will be presented by dose group. For continuous variables, data will be summarized with the number of participants (N), mean, standard deviation, median, minimum, and maximum by treatment group. For categorical variables, data will be tabulated with the number and proportion of participants for each category by treatment group.

#### 12.1 Determination of Sample size

Twelve participants will be enrolled in each arm for a total of 24 participants. A response rate of 10% or less would not be considered promising (null hypothesis) as the ipilimumab response rate in untreated patients is 10.9%. A response rate of at least 30% is promising (alternative hypothesis). Point estimates and 95% confidence intervals for the response rates will be reported. Alpha (probability of Type I error) for hypothesis tests will be 0.1. If 4 or more of 12 participants in an arm respond (response rate of 33% or greater), the treatment will be considered promising for further investigation.

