#### 12.2 Analysis Populations

## **Evaluable participants for efficacy**

• All participants who receive at least 1 dose of study drug(s) will be evaluated for the primary endpoint. Participants who develop rapid symptomatic disease progression

- or drop out early due to death will be treated as non-responders. Participants who develop early toxicities that require treatment delay or discontinuation will continue to be evaluable on study.
- Participants may be replaced in either arm if they complete randomization but do not complete any cycles of therapy.

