3.4 Determination of Sample Size

This study is not intended or powered for hypothesis testing. The study is intended to provide preliminary estimates of adverse events, response rates, effect sizes and confidence intervals. A sample size of approximately twelve participants in each arm, for a total of 24 participants, will provide these preliminary estimates. The study protocol incorrectly states that a Simon 2-stage design will be implemented for this study. A 2-stage design was not implemented; rather, a single-stage design was used.

Table 1 provides 95% exact confidence intervals for the proportion of responders per treatment arm. These confidence intervals provide information needed for the design of future studies.

Table 1: Confidence Intervals for the True Proportion of Responders

Observed responder rate	95% Confidence Interval (n = 12)
8.3% (1/12)	(0.2%, 38.5%)
16.7% (2/12)	(2.1%, 48.4%)
25.0% (3/12)	(5.5%, 57.2%)
33.3% (4/12)	(9.9%, 65.1%)

41.7% (5/12)	(15.2%, 72.3%)
50.0% (6/12)	(21.1%, 78.9%)

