5.4 Efficacy Analysis

Efficacy analyses will be conducted on the efficacy-evaluable population (see Section 5.1.1), with participants grouped according to the treatment assigned at randomization.

Per the intention-to-treat principle, data from all randomized and dosed participants, regardless of adherence to study drug or to the protocol, will be included in the efficacy analyses. Efficacy summaries will include data from participants who discontinued study drug early but continued with study assessments and may include data collected at unscheduled visits, early termination visits, or follow-up visits.

Comparisons of Interest

This study is not powered for statistical comparisons between arms.

Type I Error Management

This study is not intended or powered for hypothesis testing. Due to the exploratory nature of this study, no control of type I error will be applied for any of the endpoints.

Covariate Adjustment

Unless otherwise noted, analyses of primary and secondary efficacy endpoints will be adjusted for the following covariate:

- Previous response to PD-1 therapy (primary refractory disease, progressive disease)

Given that the above covariate is the stratification factor used when randomly allocating participants, no missing data of this baseline covariate is expected.

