5.4.1 Primary Efficacy Endpoint

The primary endpoint is the response to ipilimumab/nivolumab and ipilimumab alone by Week 18, defined as having achieved CR or PR as measured by RECIST v1.1 criteria, or a PR/CR at any time prior to Week 18.

The objective response rate (ORR) is defined as the number of participants whose best objective response (BOR) is CR or PR divided by the total number of participants in the population of interest. Participants with a BOR of stable disease (SD), progressive disease (PD) or without a post-baseline tumor assessment will be considered non-responders and, thus, will be counted in the denominator of the ORR calculation.

The BOR is defined as the best response designation, as determined by the investigator, recorded between the date of randomization and the date of subsequent anticancer therapy (including tumor-directed radiotherapy and tumor-directed surgery). For participants without subsequent anticancer therapy, all available response designations through Week 19 (Week 18 +7 day window) will contribute to the BOR assessment.

The ORR will be estimated within each treatment arm and 95% confidence intervals (CIs) will be estimated using the Clopper-Pearson method.

This study is not powered for statistical comparisons between arms. To aid in interpretation, each arm will be indirectly compared to the historical ipilimumab ORR of 10.9% (Hodi et al. 2010).

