5.4.2 Secondary Efficacy Endpoints

Disease Control Rate

DCR is defined as the proportion of participants who achieve SD, PR, or CR as measured by RECIST v1.1. That is, DCR is the number of participants whose BOR is SD, PR, or CR divided by the total number of participants in the population of interest. For SD, measurements must have met the SD criteria per RECIST v1.1 at least once after study entry, with disease assessment occurring at least 8 weeks after first study drug treatment.

DCR will be assessed at Week 12 (+7 days) and Week 18 (+7 days). DCR will be estimated within each treatment arm and 95% confidence intervals (CIs) will be estimated using the Clopper-Pearson method.

This study is not powered for statistical comparisons between arms. To aid in interpretation, each arm will be indirectly compared to the historical ipilimumab DCR of 28.5% (Hodi et al. 2010).

Time to Treatment Failure

TTF is defined as the time from first study drug treatment until the participant is started on another line of systemic therapy or participant death, whichever occurs first. Participants who are alive and do not start another therapy will be censored at the date of last follow-up. Time to event distributions will be estimated using Kaplan-Meier techniques.

Overall Survival

OS is defined as the time from first study drug treatment until death from any cause. Participants without documentation of death will be censored on the date of last contact. Time to event distributions will be estimated using Kaplan-Meier techniques.

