6 DIFFERENCES COMPARED TO PROTOCOL

- Section 3.4 (Determination of Sample Size): SAP provides additional justification for the selection of sample size.
- Section 3.4 (Determination of Sample Size): The study protocol incorrectly states that a Simon 2-stage design will be implemented for this study. The SAP clarifies that a 2-stage design was not implemented.
- Section 5.1.2 (Safety-Evaluable Population): The toxicity-evaluable population referred to in the Protocol has been modified and renamed the safety-evaluable population in the SAP. All safety analyses will be conducted on the safety-evaluable population and not the toxicity-evaluable population.
- Section 5.4.4 (Safety Analysis): Although the Protocol lists physical examination findings as a secondary safety endpoint, physical examination data will not be summarized because any significant findings should be captured and summarized as adverse events.
- Section 6.1.2 (Randomization): Although the protocol states that participants will be stratified based on melanoma subtype, this stratification factor was not implemented into the IVRS. Participants were only stratified on their previous response to PD-1 therapy (primary refractory vs progressive disease).
- Section 12 (Statistical Analysis): SAP clarifies that the statistical analyses may be performed using SAS or R statistical software.

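### Does the SAP need a stated criterion for its comparison with the historical 10.9%, now that the protocol's 4-of-12 rule sits beside a plan without hypothesis tests?

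*Protocol*

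**What the plan says.** Protocol 12.1 takes a null response rate of 10%, an alternative of 30%, an alpha of 0.1 and 12 participants per arm. It then gives the rule: "If 4 or more of 12 participants in an arm respond (response rate of 33% or greater), the treatment will be considered promising". The same section also plans point estimates with 95% confidence intervals.

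The SAP changes the footing. Section 3.4 states: "This study is not intended or powered for hypothesis testing". Section 5.4 adds that "no control of type I error will be applied for any of the endpoints". Section 5.4.1 specifies the response rate in each arm with a Clopper-Pearson 95% interval, and then says: "To aid in interpretation, each arm will be indirectly compared to the historical ipilimumab ORR of 10.9" percent. Section 5.4.2 treats disease control the same way: "each arm will be indirectly compared to the historical ipilimumab DCR of 28.5" percent. Neither section names the quantity compared or a threshold.

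SAP Section 6 lists the differences from the protocol. It withdraws the Simon two-stage design explicitly. On sample size it says only that the "SAP provides additional justification for the selection of sample size". It does not mention the null, the alternative, the alpha or the 4-of-12 rule. SAP Appendix 8.1 reprints the protocol synopsis, rule included, but that copy still carries the withdrawn Simon design. Protocol Section 12 and SAP Section 2 both say that the SAP supersedes the protocol's analysis plan.

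**The concern.** A reader who wants to know whether an arm succeeded finds a rule in one document and an undefined comparison in the other. Three readings can be constructed:

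- the observed rate exceeds 10.9%;
- the protocol's count of 4 is reached;
- the lower 95% limit exceeds 10.9%.

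They are met from 2, 4 and 5 responders respectively, so all three agree only at 0, 1, and 5 or more. If the choice were really open, the conclusion from the same data could differ, and it could be made after the responses are known. The trial is open-label, response is judged by the investigator, and the Data Review Team includes the sponsor and all active principal investigators.

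Two related points add to the impression. The 28.5% benchmark for disease control is not in the protocol. And a rule written for 12 participants is ambiguous if an arm ends with another number.

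**Working it through.** **Inputs.** n = 12 per arm, null 10%, alternative 30%, alpha 0.1, cut-off 4 (Protocol 12.1). Benchmarks 10.9% and 28.5%, Clopper-Pearson 95% limits (SAP 5.4.1, 5.4.2). Table 1 (SAP 3.4).

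**Formulas.** P(X ≥ r | p) = Σ over x from r to 12 of C(12, x) p^x (1 − p)^(12 − x). The Clopper-Pearson lower limit at x responders is the p for which P(X ≥ x | p) = 0.025.

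**The plan's own figures.**

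- At 10%, P(X ≥ 3) = 0.1109 and P(X ≥ 4) = 0.0256. So 4 is the smallest cut-off with type I error at or below 0.10. It is also the smallest at 0.05 per side, so the unstated sidedness of alpha makes no difference.
- At 30%, P(X ≥ 4) = 0.5075.
- All six rows of SAP Table 1 reproduce to 0.1 percentage point.

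**The readings side by side.**

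| Responders | Observed | 95% exact interval | Observed rate above 10.9% | 4-of-12 rule met | Lower limit above 10.9% |
|---|---|---|---|---|---|
| 1 | 8.3% | 0.2% to 38.5% | no | no | no |
| 2 | 16.7% | 2.1% to 48.4% | yes | no | no |
| 3 | 25.0% | 5.5% to 57.2% | yes | no | no |
| 4 | 33.3% | 9.9% to 65.1% | yes | yes | no |
| 5 | 41.7% | 15.2% to 72.3% | yes | yes | yes |

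The two readings that rest on something the documents plan, the rule and the 95% interval, part only at 4 of 12.

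**How often an arm lands on 4.** P(X = 4) = P(X ≥ 4) − P(X ≥ 5).

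- True rate 10.9%: 0.0341 − 0.0063 = 0.0278, or 2.8%.
- True rate 30%: 0.5075 − 0.2763 = 0.2312, or 23%.

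**Why they part there.** The one-sided tail probability at 4 of 12 is 0.0256 against 10% and 0.0341 against 10.9%. Both are below 0.10, so the rule is met against either benchmark. Both are above 0.025, so the 95% interval contains either benchmark. At 3 of 12 the tails are 0.1109 and 0.1349, and neither criterion is met. The difference is one of error level.

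**What the point-estimate reading adds.** It brings in 2 and 3 of 12. With it, the probability of a result on which the readings disagree becomes P(X ≥ 2) − P(X ≥ 5):

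- 0.3822 − 0.0063 = 0.3759 at a true 10.9%;
- 0.9150 − 0.2763 = 0.6387 at 30%.

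Nearly all of the apparent problem at 10.9%, and most of it at 30%, therefore comes from a reading that no section adopts.

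**Disease control.** The observed rate exceeds 28.5% from 4 of 12 (33.3%). The lower 95% limit exceeds it only from 8 of 12 (34.9%; at 7 of 12 it is 27.7%). The protocol has no decision rule for disease control, so there is nothing for the benchmark to contradict.

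**Arms of other than 12.** SAP 3.4 speaks of "A sample size of approximately twelve participants in each arm", and Protocol 12.2 says "Participants may be replaced in either arm if they complete randomization but do not complete any cycles of therapy". At 4 of 13, or 30.8%, the count in the rule is met but the 33% is not. Whether replacement can lead there depends on what completing a cycle means:

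- Protocol Section 8 equates one dose with one cycle. On that reading a replaced participant was not dosed and is not in the efficacy population, so replacement adds nobody to the 12.
- Table 3 gives a cycle 21 days, and SAP 5.1.2 treats completing a cycle as stricter than receiving a dose. On that reading a dosed participant can be replaced and still counted, and 13 is possible.

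**The case for a change.** The strongest case for a change is that supersession does not settle the matter. Protocol Section 12 gives the SAP precedence where the two differ, SAP Section 6 is where differences are declared, and the rule is not among them although the Simon design is. Even if the rule is taken as dropped, the comparison that replaces it has no criterion, and it is the only interpretive step in the SAP body for the primary endpoint. The protocol had tied that step to further investigation. A few sentences would close the gap at no cost in patients.

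The part about Section 6 stands: it should have said what became of the null, alpha and rule, and the appendix cannot answer, because it also reprints a design that the SAP withdraws.

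The rest carries less weight. A benchmark offered to aid interpretation in a plan that disclaims testing does not need a pass mark. Supplying one would bring back the decision rule that the SAP sets aside. The worry about a choice made after the fact is not supported by the text: SAP 4.2 describes review of safety and emerging data, and gives the team no role in judging response against 10.9%. The choice between keeping the rule as a descriptive marker and withdrawing it is a trade-off. The rule is met 51% of the time at a true 30%, and the interval criterion 28% of the time.

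**Conclusion.** No change to the plan follows. This is a gap that an analyst fills sensibly. The SAP as written yields each arm's response rate and exact 95% interval, with 10.9% beside it. The natural report says whether the interval contains 10.9% and, if the protocol's rule is mentioned, whether 4 responders were reached. No stated figure is wrong, and the response rate and its interval are the same under every reading.

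The real tension is confined to 4 of 12, with probability 2.8% at a true 10.9% and 23% at 30%. There an arm can fairly be called promising for further study while its 95% interval still includes the historical rate. Protocol 12.1 itself plans both statements.

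This rests on three assumptions:

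- The benchmark is read together with the interval, and a point estimate above 10.9% is not by itself called an improvement.
- The disease control benchmark is handled in the same descriptive way.
- Each arm has 12 evaluable participants. With 13, the count and the percentage in the rule would differ at 4 responders, and the report would need to give both. The estimate and interval would remain valid.
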